Investigational Medical Device Description	GreenBone Implant is a ceramic reabsorbable scaffold with a geometrical structure, engineered to reflect anatomical and physiological bone hierarchical structures. GreenBone Implant scaffold is made of biomimetic substituted calcium phosphate phases (HA and β -TCP and minerals). It is suitable for repair of defects in bones. GreenBone Implant is a EU class III Medical Device.

Clinical Investigation Rationale	
Bone defects can result from malformation, high-energy traumatic events, bone resection due to different pathologies such as tumors or infections, or from the treatment of complex non-unions, all very challenging conditions in orthopedic practice.
 
Current treatment of bone defects usually implies the use of bone grafts and/or biocompatible materials, to create a scaffold that bridges the defect, favoring the migration of cells from the neighboring tissues to fill the gap. Autograft and Allograft are the treatments most currently used for large bone loss, but both treatments have significant disadvantages. Different types of synthetic materials have been tested for repair of long bone gaps.
 
However, at the moment, there is not any bone substitute with the ideal/desirable osteoinductive, osteoconductive and mechanical properties. GreenBone Implant is a synthetic, acellular, reabsorbable, new generation bone graft, being suitable for surgical reconstruction of bone defects.

Study Objectives	
The primary objective of this study is to assess the safety profile of the GreenBone Implant in Patients undergoing surgery for the treatment of bone defects up to 6 cm, specifically for long bone repair. The initial phase of the study contemplates the treatment of bone defects up to 3 cm. Following DSMB interim assessment, at least 5 Patients, of the 25 patients, with a longer bone defect (> 3 up to 6 cm) will be enrolled.
 
The secondary objectives of this study are:
 
- To evaluate the progression of bone healing and bone regeneration at the level of the intervention site after use of GreenBone Implant throughout a 12-month observation period;- To evaluate the degree of pain throughout a 12-month observation period;- To evaluate the functional recovery of Patient throughout a 12-month observation period.- To evaluate the health related quality of life of Patient throughout a 12-month observation period.

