Study Endpoints	
Secondary Endpoints:
 
1. Evaluation of technical success, defined as successful delivery of the GreenBone Implant in the target defect bone evaluated at V2 (during surgical procedure).2. Evaluation of the bone regeneration in the area of intervention in comparison to baseline (V1), by means of X-ray examination, on visits V3, V4, V5, V6, V7 and V8. X-ray scoring systems have been implemented according to the criteria proposed by Lane and Sandhu (bone formation, union and remodeling) (Lane 1987) (See Appendix 1).3. Evaluation of the bone regeneration in the area of intervention in comparison to baseline (V1), by means of CT scan examination on visits V6 and V8 if indicated.4. Functional Assessment: evaluation of functional recovery of Patient, by means of a standardized questionnaire (36-Item Short Form Survey – SF-36), on visits V1, V3, V4, V5, V6, V7 and V8 (See Appendix 2).5. Evaluation of degree of pain perceived by the Patient, by means of a VAS (0-10 point scale), on visits V1, V3, V4, V5, V6, V7 and V8 (Price 1983) (See Appendix 3).6. Evaluation of Quality-of-Life by means of EuroQoL EQ-5D-5L Validated Questionnaire, on visits V1, V3, V4, V5, V6, V7 and V8 (See Appendix 4).7. Evaluation of global tolerability to treatment of Patient (by the Investigator), through a standardized questionnaire, on visits V3, V4, V5, V6, V7 and V8 (See Appendix 5).8. Evaluation of the number of re-interventions occurring for the Patient throughout the 12-month observation period.

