Statistical Analysis	
A descriptive analysis of safety and performance variables will be performed.
 
The descriptive analyses will be performed in order to describe the nature of adverse events, their distribution and frequency. Moreover, all factors which may appear predictive for the rate of adverse events will be analyzed (age, sex, dimension of the implanted device, system used, diabetes history, smoking habits, alcohol consumption, concomitant treatments/diseases, other). If the percentage of Patients with device-related AE would be sufficiently large in respect to the overall sample ($\geq 70\%$) to allow an evaluation of the time interval between the date of surgery and the date of the first adverse event occurrence, a median of the time interval will be estimated, with 95% Confidence Interval, through the Kaplan-Meier survival analysis.
 
An adaptive interim analysis will be performed when the first 7 Patients will have completed the 6-month follow-up visit. An independent Data Safety Monitoring Board (DSMB) will review the results of the interim analysis with respect to the primary endpoint (safety), and provide one of the following recommendations to the Sponsor: a) to stop the study for unacceptable frequency and severity of adverse events or b) to continue the study up to a minimum of 25 Patients recruited and to include at least 5 Patients with a longer bone defect (> 3 up to 6 cm).
 
The independent DSMB will receive all the safety data at regular intervals and the data about Serious Adverse Events (SAE) as soon as reported, to protect Patients participating in the study.

Investigational Sites	The study will involve 8 investigational sites in Bosnia & Herzegovina, Israel, Italy, Serbia, Slovenia, Switzerland and UK.

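### The plan has no rule for X-ray and CT healing scores after a re-intervention, so union reached after a second operation could count in the implant's healing results

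*Combined protocol and SAP*

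**What the plan says.** All references are to the Study Synopsis of the combined protocol and SAP.

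- **Objective (Study Objectives).** The first secondary objective concerns "bone healing and bone regeneration at the level of the intervention site after use of GreenBone Implant" over 12 months. The objectives on pain, functional recovery and quality of life cover the same period but do not mention use of the implant.
- **Imaging (Study Endpoints, secondary endpoints 2 and 3).** Endpoint 2 is "Evaluation of the bone regeneration in the area of intervention in comparison to baseline (V1), by means of X-ray examination", where V1 is the pre-operative visit. It is assessed at V3 to V8 and scored by the Lane and Sandhu criteria (formation, union, remodelling). CT is assessed "by means of CT scan examination on visits V6 and V8 if indicated".
- **Patient-reported outcomes (secondary endpoints 4 to 6).** SF-36, VAS and EQ-5D-5L are collected at V1 and at V3 to V8.
- **Re-intervention (secondary endpoint 8).** "Evaluation of the number of re-interventions occurring for the Patient throughout the 12-month observation period". The term is not defined, and the endpoint is not linked to any of the others.
- **Analysis (Statistical Analysis).** The only statement covering the performance endpoints is "A descriptive analysis of safety and performance variables will be performed".

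No section says whether values recorded after a re-intervention are included, excluded, counted as failure or shown separately, or whether a re-operated patient stays on the visit schedule.

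**The concern.** The imaging endpoint is tied to a location, the area of intervention, and to a fixed pre-implant baseline. It is not tied to the original implant still doing the work. Suppose a patient's bone fails to heal, the site is operated on again, and it then unites. The month-12 X-ray of that patient satisfies the endpoint as worded. Yet the objective asks about healing after use of this device, and that patient is better described as a device failure followed by a successful second procedure.

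In a randomised trial, a control arm with its own re-operations would give some reference. Here there is none. Reporting the number of re-interventions separately does not repair the healing summary, because a total does not show which of the united patients had been re-operated.

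Silence also leaves the choice open until after the data of an open-label study have been seen. These endpoints are secondary, but they carry the study's evidence on performance, which its title names alongside safety.

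**Working it through.** **1. Inputs from the documents.** Study Sample Size gives 25 patients including a 20% drop-out allowance. The number evaluable is not stated; 25 × (1 − 0.20) = 20, and back again 20 / (1 − 0.20) = 25. The size was chosen by analogy with other first-in-human studies, so there is no power calculation to reproduce.

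**2. Not in the documents.** There is no expected union rate, no expected re-intervention rate, and no definition of a healed proportion. The step below therefore assumes that union is summarised as a proportion at V8 and that 80% show union. Only the differences matter, and they do not depend on the 80%.

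**3. Effect of the handling rule.** Let *n* be the denominator, *x* the number united at V8, and *k* the number of those whose union followed a re-intervention.

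- As observed: *x*/*n*
- Re-intervention counted as not united: (*x* − *k*)/*n*
- Difference: *k*/*n*, which is 1/25 = 4 points or 1/20 = 5 points per patient

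**4. Range.** Exact (Clopper-Pearson) 95% limits for *y* successes in *n* are the 0.025 quantile of Beta(*y*, *n* − *y* + 1) and the 0.975 quantile of Beta(*y* + 1, *n* − *y*).

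| k | n = 25 | 95% CI | n = 20 | 95% CI |
|---|---|---|---|---|
| 0 (as observed) | 20/25 = 80% | 59.3–93.2 | 16/20 = 80% | 56.3–94.3 |
| 1 | 19/25 = 76% | 54.9–90.6 | 15/20 = 75% | 50.9–91.3 |
| 2 | 18/25 = 72% | 50.6–87.9 | 14/20 = 70% | 45.7–88.1 |
| 3 | 17/25 = 68% | 46.5–85.1 | 13/20 = 65% | 40.8–84.6 |
| 4 | 16/25 = 64% | 42.5–82.0 | 12/20 = 60% | 36.1–80.9 |
| 5 | 15/25 = 60% | 38.7–78.9 | 11/20 = 55% | 31.5–76.9 |

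**5. Direction.** For union, *k*/*n* cannot be negative, so the as-observed proportion is never below the one that counts re-intervention as failure. That argument does not carry over to VAS, SF-36 or EQ-5D-5L. A patient re-operated shortly before a visit may score worse, and one re-operated long before it may score better.

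**The case against.** The strongest reply is that the plan states no rule at all. The endpoint list says when assessments take place, and the analysis section promises only description. Separating or excluding values after a re-intervention is as compatible with that text as pooling them. A reader might infer that the plan summarises every score regardless of re-intervention and so credits the second operation to the implant. The documents do not say that, and it would be wrong to report it as their rule. What stands is narrower: a summary of all scheduled visits is a natural way to carry out the text, and nothing in the text prevents it.

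A reader might also infer that the bias always favours the device. That is not supported either. It holds for a union proportion compared with counting re-intervention as failure, but pain and quality of life can move either way.

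Three further objections are sound and shape the remedy.

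- Re-intervention is undefined and could include removing hardware from a bone that has already united. Counting every such procedure as failure would misclassify healed patients.
- Restricting the main patient-reported summary to values before re-intervention would leave the month-12 figures resting on patients who never needed a second operation, which can itself flatter the device. The objectives for these outcomes do not refer to use of the implant, so keeping all follow-up is a legitimate choice.
- The documents specify a count of re-interventions but do not say that dates are recorded.

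Finally, these endpoints are secondary and descriptive, with no test or success threshold; the primary endpoint is adverse events. Re-interventions are also reported in their own right, so failures are not hidden, only unlinked from the scores. This limits the weight of the point without removing it.

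**Conclusion.** The point holds for the imaging endpoints as a gap with a foreseeable consequence. The plan anticipates re-interventions, scores healing at the site by scheduled visit, and gives no rule for values after a second operation. Summarised as observed, union reached after re-intervention would count in the implant's healing results, with no comparator to offset it.

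The size is 4 percentage points per affected patient with all 25, or 5 points with 20 evaluable. This rests on two assumptions: that union is summarised as a proportion, which the plan does not specify, and that the drop-out allowance implies 20 evaluable patients. It shows sensitivity and is not a forecast.

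For pain, function and quality of life, the conclusion is only that the handling should be stated. The available text is a synopsis without its appendices; a rule elsewhere in the protocol, for example with the X-ray scoring in Appendix 1, would settle the point. Otherwise this is a worthwhile, inexpensive improvement and does not undermine the study's primary aim.

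**What to change.** Add the following to the analysis plan before the data are summarised.

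1. **Definition.** For analysis, define an index-site re-intervention as one for failed healing or an implant problem. List separately other procedures, such as hardware removal in a bone already united.
2. **Imaging.** Make union without such re-intervention the main summary of X-ray and CT healing, counting a patient as not united from the date of the re-intervention. Show the as-observed Lane and Sandhu scores beside it.
3. **VAS, SF-36 and EQ-5D-5L.** Keep the as-observed by-visit summary as the main one. Add a supportive summary restricted to values before re-intervention, and give the number of patients already re-intervened at each visit.
4. **Data.** Record the date of each re-intervention, and the reason for it, if they are not already captured. Flag affected patients in the listings.

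The cost is some analysis wording, one or two extra tables and possibly a date field. Visits and sample size do not change. The downside for the sponsor is a healing figure that may be less favourable.

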STUDY SYNOPSIS

Study Title	A pre-market, multi-center, international, open-label, single-arm study to evaluate the safety and performance of a Class III medical device (GreenBone Implant) for surgical repair of long bone defects
Study Code	GB-02-18
Study Sponsor	GreenBone Ortho S.r.l. [name] – Italy
Clinical Phase	Pre-market clinical investigation of a Class III Investigational Medical Device.
Study Design	Multi-center, international, prospective, open-label, single-arm, first-in-human clinical investigation. The Patients enrolled in this clinical investigation will undergo a scheduled surgery for the treatment of long bone defects up to 6 cm using GreenBone Implant. After the surgery, the Patients will be monitored at pre-scheduled visits up to 12 months. Adverse events, pain, quality of life and functional parameters, as well as X-ray and CT scan, will be evaluated at scheduled follow-up visits. An independent DSMB will review the safety reports at regular intervals and Serious Adverse Events (SAE) as soon as reported, to protect Patients participating in the study. The initial phase of the study contemplates the treatment of bone defects up to 3 cm. An adaptive interim analysis will be performed when the first 7 Patients will have completed the 6-month follow-up visit. The DSMB will review the results of the interim analysis with respect to the primary endpoint (safety), and provide one of the following recommendations to the Sponsor: a) to stop the study for unacceptable frequency and severity of adverse events or b) to continue the study up to 25 Patients recruited and to include at least 5 Patients with a longer bone defect (> 3 cm up to 6 cm).
Investigational Medical Device	GreenBone Implant for bone substitution, a Class III Medical Device. The GreenBone Implant had not yet received the CE mark at the time of the Study first submissions and first patient enrollment. The Device received the CE mark in December 2019.
Investigational Medical Device Use	GreenBone Implant is used in the surgical procedures for repair of bones defects.

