Implant of the Investigational Medical Device	
GreenBone Implant is applied to the bone gap by the surgeon during the scheduled intervention, according to standard clinical practice and to the information provided by GreenBone Ortho S.r.l. in the device Instructions For Use (IFU) document.

Study Population	
Male and female Patients, aged between 18 and 65 years, undergoing surgery for the treatment of long bone defects up to 6 cm.
 
Please note: The initial phase of the study contemplates the treatment of bone defects up to 3 cm. After an adaptive interim analysis review by the DSMB, inclusion criteria will be amended; specifically to include the recruitment of patients suffering from bone defects up to 6 cm.

Study Sample Size	In the absence of published guidance on first-in-human trials on long bone surgery, the sample size (n=25 including a 20% drop-out rate) has been chosen to be consistent with first-in-human studies of pharmacological agents which are usually conducted in 10-15 patients (Rubinstein LV et al 2010).
Inclusion Criteria	
1. Male or female Patients.2. Patients aged ≥ 18 and ≤ 65 years old.3. Patients requiring long bone defect reconstructions up to 3 cm, resulting from high-energy traumatic events, or from the treatment of complex bone non-unions in the extremities (arms and legs), or patients undergoing the second stage of the Masquelet technique.4. Patients understanding the nature of the study and providing their informed consent to participation.5. Patients willing and able to attend the follow-up visits and procedures foreseen by study protocol. 
Please note: after interim analysis review by the DSMB, inclusion criteria n. 3 will be modified as follows (all Investigators will be notified by the Sponsor, and adequate training by CRA will be conducted):
 
Change of inclusion criteria n. 3: Patients requiring long bone defect reconstructions up to 6 cm, resulting from high-energy traumatic events, or from the treatment of complex bone non-unions in the extremities (arms and legs), or patients undergoing the second stage of the Masquelet technique.

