Exclusion Criteria	
For the specific characteristics of this study, the final decision on Patient enrolment will be made by the Investigator at time of surgery (during surgery, before implantation).
 
1. Patients with bone infection at the time of enrolment.2. Patients with bone malignant tumor(s) at the time of enrolment.3. Patients who have been treated with chemotherapy or radiotherapy within 12 months before the enrolment.4. Patients with concomitant infectious systemic diseases at the time of enrolment.5. Patients with known inflammatory systemic diseases at the time of enrolment.6. Patients with concomitant myeloproliferative disorders at the time of enrolment.7. Patients currently treated with systemic immunosuppressive agents, excluding steroids.8. Patients with active autoimmune disease.9. Patients with a pre-existing calcium metabolism disorder (i.e. hypercalcemia).10. Known hyperthyroidism or autonomous thyroid adenoma.11. Patients with coagulopathy or bleeding disorders.

	
12. Patients who are not allowed to undergo the study procedures involving imaging (X-rays, CT scan) based on Investigator's judgement.
 
13. Patients with known or suspected allergy or hypersensitivity to the GreenBone Implant components.
 
14. Patients who are participating or have participated in other clinical studies within the 30 days before the study enrolment.
 
15. Patients identified by the Investigator to have intra-operative findings that may preclude conduct of study procedure.
 
16. Patients with occurrence of major intra-operative complications that require resuscitation or deviation from the planned surgical procedure.
 
17. Women who are pregnant or breast-feeding or who wish to become pregnant during the period of the clinical investigation and for three months later.
 
18. Female Patients of childbearing age (less than 24 months after the last menstrual cycle) who do not use adequate contraception *.
						

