	Visit 6 (V6 – Control 4)	
 X-Ray examination CT scan examination (if healing activity inconclusive on radiographs) Evaluation of global tolerability of Patient (by the Investigator) Quality of Life (EuroQoL EQ-5D-5L Validated Questionnaire) VAS score (0-10 point scale) Functional assessment (36-Item Short Form Survey – SF-36) Concomitant medications Adverse events 	D +180 ±14 (6M)
	Visit 7 (V7 – Control 5)	
 X-Ray examination Evaluation of global tolerability of Patient (by the Investigator) Quality of Life (EuroQoL EQ-5D-5L Validated Questionnaire) VAS score (0-10 point scale) Functional assessment (36-Item Short Form Survey – SF-36) Concomitant medications Adverse events 	D +270 ±14 (9M)
	Visit 8 (V8 – Control 6)	
 X-Ray examination CT scan examination (if healing activity inconclusive on radiographs) Evaluation of global tolerability of Patient (by the Investigator) Quality of Life (EuroQoL EQ-5D-5L Validated Questionnaire) VAS score (0-10 point scale) Functional assessment (36-Item Short Form Survey – SF-36) Concomitant medications Adverse events 	D +360 ±14 (12M)

	Should any of the Patients request at any time an additional visit (i.e. in case of discomfort in the area of intervention), an additional visit should be organized to allow examination by the Investigator.
Study Endpoints	
Primary Endpoint:
 
Evaluation of adverse events rate during the study period. All adverse occurrences (serious/non-serious or device-related/non device-related) will be recorded prospectively, categorized and evaluated for causality using defined criteria.
 
The study will be monitored by an independent Data Safety Monitoring Board (DSMB).

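### Does the safety analysis need a stated adverse event summary split at the 3 cm defect length that stages enrolment?

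*Combined protocol and SAP*

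**What the plan says.** All references are to the synopsis of the combined protocol and SAP, the only part supplied.

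- **Study Design.** "The initial phase of the study contemplates the treatment of bone defects up to 3 cm". When the first 7 patients have completed the 6-month visit, the DSMB reviews safety. It recommends either stopping or continuing and "to include at least 5 Patients with a longer bone defect", meaning over 3 and up to 6 cm.
- **Inclusion Criteria, item 3.** Until the interim review, the criterion admits "Patients requiring long bone defect reconstructions up to 3 cm". After the interim review the limit becomes 6 cm.
- **Study Objectives.** There is one primary objective: to "assess the safety profile of the GreenBone Implant in Patients undergoing surgery for the treatment of bone defects up to 6 cm".
- **Study Endpoints.** The primary endpoint is "Evaluation of adverse events rate during the study period", with no subdivision by defect length.
- **Statistical Analysis.** The analyses are descriptive, to "describe the nature of adverse events, their distribution and frequency". The entry then adds that "all factors which may appear predictive for the rate of adverse events will be analyzed (age, sex, dimension of the implanted device", followed by several other patient and treatment factors and an open category. The DSMB also receives safety data at regular intervals and serious events as they are reported.

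**The concern.** The design treats 3 cm as a safety boundary: nobody above it is treated until a board has reviewed the patients below it. One would expect the final safety report to use the same boundary, and the synopsis does not say that it will.

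The interim review cannot fill that gap. The first 7 patients all come from the phase limited to 3 cm, so the review contains no data on larger defects. Evidence on the patients it releases comes only afterwards. If adverse events were then reported only as one rate for all patients, a conclusion worded for defects up to 6 cm could rest mainly on defects up to 3 cm. A reader could not see how little had been observed above that length.

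**Working it through.** **Inputs.** The total is 25 patients (Study Sample Size), at least 5 of them over 3 cm (Study Objectives), and the first 7 are all at or below 3 cm (Study Design). I take exactly 25 recruited. Study Design words the total as a ceiling of 25 and Statistical Analysis as a minimum of 25; a larger total would change the split. The plan gives no adverse event rate, precision target or interval for that rate, so it has no figure of its own to reproduce here.

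**Step 1: weight of the smaller defects in a pooled rate.** With k patients over 3 cm, the weight at or below 3 cm is (25 − k)/25.

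- k = 5 (the minimum): 20/25 = 80%
- k = 10 (illustrative): 15/25 = 60%
- k = 18 (at most 25 − 7): 7/25 = 28%

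The 80% figure is therefore the extreme case. The value 18 is an upper bound, because any further small-defect patient enrolled would lower it.

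**Step 2: what zero events would show.** The exact two-sided 95% upper limit for 0/n is 1 − 0.025^(1/n).

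| n | Upper limit for 0/n |
|---|---|
| 25 | 13.7% |
| 20 | 16.8% |
| 18 | 18.5% |
| 10 | 30.8% |
| 5 | 52.2% |

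The contrast between 13.7% and 52.2% is real. It comes from enrolling few larger defects, and tabulating them separately does not change it. The synopsis also plans no confidence interval for the adverse event rate. The only interval it mentions is for a median time to first event, under a condition. The 13.7% is thus not a figure the plan undertakes to report.

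**Step 3: what 5 patients can reveal.** The chance of seeing at least one event of a type with true rate p is 1 − (1 − p)^5. This is 41.0% at p = 10% and 67.2% at p = 20%. Separate display would be honest, but it could not establish or exclude a difference by size.

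**Step 4: could pooling hide a signal?** Take assumed counts of 2/20 at or below 3 cm and 2/5 above.

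- Separately: 10.0% (95% CI 1.2 to 31.7%) and 40.0% (5.3 to 85.3%).
- Pooled: 4/25 = 16.0% (4.5 to 36.1%).

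The pooled upper limit lies below the 40% observed above 3 cm, which looks striking. But with 4 events among 25 patients, Fisher's exact two-sided p sums the tables with 2, 3 or 4 events in the group of five: (1900 + 200 + 5)/12650 = 2105/12650 = 0.17. The example is compatible with no effect of size, and its counts are invented. It shows no error in the plan.

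**Step 5: does the plan ignore size?** It does not. Statistical Analysis names implant dimension third in its list of factors for the adverse event rate. The synopsis does not equate implant dimension with defect length, but it is a close proxy. It has no cut-point, method or interval, and neither has any other factor listed.

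**Step 6: will the grouping be available?** After the interim, criterion 3 alone does not show on which side of 3 cm a patient falls. The quota of at least 5 does require that classification, so the sponsor must hold it for every patient. The Exclusion Criteria entry adds that "the final decision on Patient enrolment will be made by the Investigator at time of surgery", which offers a natural time to fix the group.

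**The case for a change.** The best case for a change is that naming implant dimension does not amount to reporting by enrolment stage. An analyst could relate adverse events to device size in full without ever stating how many patients with defects over 3 cm had one. In a first-in-human study whose primary objective is safety, the boundary that controls enrolment deserves its own table column. The cost would be one table split and a few sentences. The small group is a reason to show its uncertainty, not to leave it inside a total.

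Much of this stands. No 3 cm summary is stated, implant dimension is not defined as defect length, and a split by stage would be good reporting practice. It would need a caveat that defect group is confounded with enrolment period, since larger defects enter only after the interim.

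It falls short of showing a fault. The text does not confine the analysis to a single overall rate: it speaks of distribution as well as frequency and commits to analysing size. Only a synopsis was supplied, and adverse event table layouts would normally sit in fuller analysis text. Patients above 3 cm are not unobserved either, because nothing limits the DSMB's regular safety review to the period before the interim.

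**Conclusion.** No change to the plan follows. Carried out as written, this descriptive analysis yields no wrong number, test or decision rule. What is left is that one listed factor has no stated cut-point, in a synopsis that gives no such detail for any factor. An analyst working on a study staged at 3 cm would naturally show adverse events on either side of 3 cm, and the quota ensures that the grouping is known.

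The largest consequence is one of presentation. If only 5 of 25 patients exceed 3 cm, 80% of a pooled rate reflects smaller defects, and zero events in the larger group would still allow a true rate up to 52.2%. Readers of the eventual report should keep that in mind, but a stated split would display the limitation without reducing it.

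This rests on a total of exactly 25, on the minimum quota for the 80% and 52.2% figures, and on the synopsis alone. With more patients over 3 cm, up to the bound of 18, the weight of smaller defects falls to 28% and the zero-event limit for the larger group to 18.5%.

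### The Kaplan-Meier time to first AE is estimated only if at least 70% of patients have a device-related AE, and the timed event is not clearly named

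*Combined protocol and SAP*

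**What the plan says.** The Statistical Analysis row of the synopsis plans a descriptive safety analysis that will "describe the nature of adverse events, their distribution and frequency". It adds one time-to-event summary, subject to a condition: "If the percentage of Patients with device-related AE would be sufficiently large in respect to the overall sample", with 70% or more given as the level, then "a median of the time interval will be estimated, with 95% Confidence Interval", by Kaplan-Meier. The interval runs "between the date of surgery and the date of the first adverse event occurrence".

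The condition therefore names device-related AEs, while the interval names adverse events without qualification. The primary endpoint keeps the two categories apart: "All adverse occurrences (serious/non-serious or device-related/non device-related) will be recorded prospectively".

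The Study Sample Size row gives "n=25 including a 20% drop-out rate". The text does not say whether the overall sample is the 25 patients recruited, those implanted, or those who complete. Re-interventions (secondary endpoint 8) are counted, not timed. The supplied synopsis names no other time-to-event safety summary.

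**The concern.** A Kaplan-Meier analysis allows for patients who leave early. Here it appears only when device-related AEs are very common, so at lower event rates no named method handles unequal follow-up, although 20% drop-out is planned and AEs are the primary endpoint.

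A minimum event share can make sense for a median. It makes none for cumulative incidence at a fixed time, which can be estimated at any event count.

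The wording adds a second problem. If the timed event is any first AE, the analysis depends on a different and narrower event than the one it describes.

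**Working it through.** **Inputs.** From the documents: n = 25, 20% drop-out, the 70% threshold, and V8 at Day 360 ± 14 (Days 346 to 374). The documents give no device-related AE rate, so 12-month risks of 20% to 70% are assumed. The plan shows no derivation of the 70%, so there is no figure of its own to reproduce.

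**1. What the threshold requires.** 0.70 × 25 = 17.5, so 18 patients. If completers are meant: 25 × 0.8 = 20, and 0.70 × 20 = 14 patients.

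**2. Is 70% sensible for a median with a confidence interval?** With complete follow-up and d events in n, S = 1 − d/n at the end. The upper limit of the median is finite only if the upper 95% limit of S is at or below 0.5. On the log-log scale that limit is exp(−exp(L − 1.96·se)), where L = ln(−ln S) and se = √[d/(n(n−d))] / |ln S|.

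| Events | S | Upper limit of S | Upper limit of median |
|---|---|---|---|
| 17 of 25 | 0.32 | 0.502 | open |
| 18 of 25 | 0.28 | 0.460 | finite |
| 14 of 20 | 0.30 | 0.501 | open |
| 15 of 20 | 0.25 | 0.449 | finite |

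So the level fits on the 25-patient reading and just misses on the 20-completer reading.

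**3. How often the condition is met, and what it withholds.** With complete follow-up, the median itself is reached at 13 of 25 events. Two binomial probabilities follow: P(X ≥ 18) that the condition is met, and P(13 ≤ X ≤ 17) that a median is reached but not reported.

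| Assumed 12-month risk | Condition met | Median reached, not reported |
|---|---|---|
| 20% | <0.01% | 0.04% |
| 30% | <0.01% | 1.7% |
| 40% | 0.12% | 15% |
| 50% | 2.2% | 48% |
| 60% | 15% | 69% |
| 70% | 51% | 47% |

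A simulation added drop-out: constant event hazard, 20% exponential drop-out by Day 360, V8 spread evenly over Days 346 to 374, threshold 18 of 25. A median reached by Day 346 but not reported then occurs in 14%, 44% and 73% of trials at risks of 40%, 50% and 60%. At 30% or below almost no median is lost.

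**4. If the timed event is any AE.** Suppose all 25 patients have an AE and 17 have one that is device-related. Then 17/25 = 68%, which is below 70%, and the time to first AE is not estimated although every patient had the event.

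**5. Size of the drop-out bias.** Under constant hazards the expected crude proportion is h/(h+g) × [1 − exp(−(h+g))], with h = −ln(1 − r) and g = −ln(0.8). For r = 0.40: h = 0.511, g = 0.223, h/(h+g) = 0.696, and exp(−(h+g)) = 0.6 × 0.8 = 0.48. The result is 0.696 × 0.52 = 36.2%. If 75% to 90% of events fall in month 1, it is 38.6% to 39.2%.

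**6. How cumulative incidence performs.** In the same simulation, Day 346 Kaplan-Meier risk averages 19.3%, 38.8% and 58.6%, in line with the true Day 346 values at 12-month risks of 20%, 40% and 60%. Coverage is 95% to 96%, and median interval width is 34 to 39 points. Root-mean-square error for the Day 346 risk, crude against Kaplan-Meier, in points: 7.8 v 8.4 at 20%, 9.2 v 9.7 at 30%, 10.2 v 10.3 at 40%, 10.8 v 10.7 at 50%, 11.3 v 10.6 at 60%.

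**7. Why Day 346.** It opens the V8 window, so no completer is censored before it. At a 20% risk the mean number at risk falls from 16.3 at Day 346 to 8.3 at Day 360.

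**The case against.** The strongest defence is that the condition fits the statistic promised. The plan offers a median with a confidence interval, and 18 of 25 is the first count at which both limits are finite. Declining to report a median with an open upper limit is a defensible choice. This stands for 25 fully followed patients, so a reader who infers that the 70% is arbitrary goes too far. It does not stand for 14 of 20, and it says nothing about cumulative incidence.

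A reader might also infer that the primary endpoint goes unanalysed below 70%. The documents do not support that: the nature, distribution and frequency of AEs are described regardless. The endpoint is also called a rate, which is left undefined and could be per patient-time, and the distribution of AEs may include timing. Nor can one say that the full plan lacks a method for unequal follow-up, since only the synopsis was supplied.

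It is tempting to claim that Kaplan-Meier would be more accurate. It removes bias but adds variance: up to about 50% risk the crude proportion has equal or slightly lower overall error. The large figures for withheld medians also need assumed risks of 50% or more.

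Finally, condition and interval share one sentence, so first device-related AE is the natural reading of the timed event. That is probably right, but the text does not say it, and the primary endpoint distinguishes the two categories.

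**Conclusion.** The point holds as a minor, cheap improvement. The 70% condition is defensible for a median with a finite upper limit in 25 fully followed patients. It is not on the 20-completer reading, and it is no reason to withhold cumulative incidence. If any AE is the timed event, the condition rests on the wrong event.

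The gain is removal of a modest downward bias (40% showing as 36.2% under constant hazards, less if events come early) and a safety timing summary that is always reported. It is not lower overall error at low to moderate risk.

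This rests on assumed AE rates, on the drop-out and visit-date model stated in the working, and on the synopsis alone. The interim stop/continue recommendation does not depend on this analysis.

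**What to change.** - Remove the 70% condition.
- Name the timed event as first device-related AE, and report first AE of any kind as a separate line.
- For each, report Kaplan-Meier cumulative incidence from surgery in all implanted patients, censored at last contact, with log-log 95% CI and numbers at risk, at 6 months and at Day 346.
- If no event has occurred by a time point, give the exact upper limit 1 − 0.025^(1/n), with n the number still followed: 13.7% for 0 of 25, 16.8% for 0 of 20.
- Report the median if the curve reaches 50%, with an open upper limit where needed; otherwise state that it was not reached.

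The cost is a few sentences and one small table (two events at two time points). The planned interval already needs the surgery and AE dates. The intervals will be wide, about 34 to 39 points at Day 346, and should be presented as such.
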